10.1. Adverse Events

All AEs, non-TEAEs, TEAEs, and SAEs will be coded using the MedDRA v. 21.0 (or later). For definitions of AEs see Table 5.

A summary table will present:

- All AEs
- Non-TEAEs
- TEAEs

[figure not shown]
- TEAEs related to study drug
- Mild TEAEs
- Moderate TEAEs
- Severe TEAEs
- TEAEs leading to withdrawal of study drug
- TEAEs resulting in death
- Serious TEAEs
- Treatment emergent SAEs related to study drug
- TEAEs with IRRs
- TEAEs with Infections
- Mild infections
- Moderate infections
- Severe infections

For summary tables the incidence of the safety event of interest (i.e. AE, TEAE, non-SAE) and the number of patients with at least one safety event of interest will be given. A patient with more than one occurrence of the same safety event of interest will be counted only once in the total of those experiencing this safety event.

Information grouped by severity (mild, moderate, severe) will be presented by the worst severity per patient. Any AEs with a missing severity will be reported in the "missing" category grade.

The following safety events of interest will be provided in summary tables grouped by MedDRA system organ class and preferred term (coded using MedDRA v. 21.0 or later):

- AEs
 - overall
 - by severity
- TEAEs
 - overall
 - by severity
 - by relationship to the study drug
- Non-TEAEs
 - overall
- Non-SAEs
- overall
- pre-conditioning TEAEs
 - overall
 - by severity
 - by relationship to the study drug
- post-conditioning TEAEs

- overall
- by severity
- by relationship to the study drug

In the AE data listings, all AEs will be displayed. AEs that are treatment-emergent will be flagged. Additional listings for pre-conditioning and post-conditioning AE will be displayed.

10.1.1. Adverse Events Leading to Study Drug Withdrawal

A summary of incidence rates (percentages) of TEAEs leading to study drug withdrawal and preferred term will be displayed as specified in Table 3.

A data listing of AEs leading to withdrawal of study drug will also be provided, displaying details of the event(s) captured on the CRF.

10.1.2. Deaths and Serious Adverse Events

TEAEs resulting in death will be listed and tabulated by preferred term.

Serious TEAEs will be tabulated by system organ class and preferred term separately for overall, by pre-conditioning and post-conditioning.

10.1.3. Treatment-Emergent Adverse Events with Infections

The number and percentage of patients reporting infections, by SOC and preferred term, and by severity will be tabulated separately for pre-conditioning and post-conditioning infections.

10.1.4. Infusion-related reactions

Infusion-related reactions will be tabulated by system organ class and preferred term.

[figure not shown]
10.2. Clinical Laboratory Evaluations

10.2.1. Hematology, Coagulation and Clinical Chemistry

The number of patients with clinical laboratory values below, within, or above the normal range by visit and in relation to baseline will be tabulated for each clinical laboratory analyte (shift table). Denominator of the percentages will be the number of patients in the All Treated Analysis Set. Clinical chemistry, hematology, and coagulation results will be presented in separate tables.

Box and whisker plots for each parameter under clinical chemistry, hematology and coagulation will be produced to display absolute values over time.

All laboratory data will be provided in data listings. Laboratory data will be listed by patient

number and visit, and flagged according to pre/post-conditioning. Laboratory values that are outside the normal range will be flagged in the data listings.

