9.2.4 Managing Abnormal Laboratory Test Values

All laboratory tests (hematology, coagulation, blood chemistry) will be captured in the database from the local laboratory.

Laboratory test abnormalities must be considered as AEs and recorded on specific AE pages of the CRF only if they:

- require specific intervention for correction, or
- lead to a change in study medication (e.g., dose modification, interruption or permanent discontinuation), or
- qualify as grade 4 severity as per modified WHO toxicity scale

If a laboratory test abnormality leads to a new clinical diagnosis, the new clinical diagnosis should be reported as an AE rather than the laboratory abnormality.

Laboratory test abnormality that qualifies as an AE as per the definition above, will follow the AE/SAE reporting process described in this section.

Laboratory abnormalities which are considered to be part of HLH signs and symptoms (see Section 9.2.1) will not be reported as AEs. If laboratory abnormalities are indicative of an HLH reactivation or worsening, the reactivation or worsening of HLH will be reported as the AE, and not the laboratory abnormalities themselves.

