As to the development of infections caused by pathogens known to be favored by the absence of IFNy biological activity, a reactivation of HZV (which resolved after a normal course with no sequelae) was observed in one healthy volunteer, at a dose of 3 mg/kg; and one HLH patient enrolled in the NI-0501-04 study developed a disseminated histoplasmosis which resulted in treatment discontinuation. This infection resolved with adequate antifungal therapy, even though emapalumab was still at detectable concentrations in blood.

Other infections reported during or after administration of emapalumab are the same ones commonly observed in immunocompromised patients or are the same ones described in pediatric populations (seasonal viral infections). Patients with active infections (except for the exclusionary ones) were enrolled and treated in the study. The presence of active infections did not lead to the discontinuation or dose decrease of emapalumab treatment, and infections resolved on study drug when treated appropriately and not associated with a refractory disease status. Severe or serious infections were generally reported in patients with previous recent significant exposure to immunosuppressive treatments as they added an additional risk factor for infection development. Importantly, emapalumab treatment has not been associated with myelosuppression.

Active infections, as per patient's clinical presentation, must be carefully followed over time, including quantitative monitoring (e.g. viral loads, antigenemia, antigenuria), when relevant.

For more details refer to the latest Investigator's Brochure (currently version 10.0, dated 24 January 2020).

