11.3.2 Safety Data

All data relating to safety will be listed and summarized using descriptive statistics.

AEs will be coded and tabulated by body system, and by individual events within each body system. AEs will also be tabulated by severity and relationship to the study medication. Summaries will also be produced for SAEs and AEs leading to withdrawal of treatment.

For each clinical laboratory test, individual patient values will be listed and summarized and change from pre-treatment baseline values calculated and summarized. Any values outside the standard reference range will be flagged. Summaries of marked abnormalities and shift tables or boxplots will be tabulated for each laboratory test.

In addition, other exploratory analyses of safety data, including summaries for different subsets of patients, may be conducted.

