2.2.2. Safety Endpoints

Safety and tolerability of emapalumab will be assessed as follows:

• Incidence, severity, causality and outcomes of adverse events (AEs) (serious and non-serious).

- Evolution of relevant laboratory parameters, e.g., complete blood cell (CBC) count, liver and renal function tests, and coagulation parameters.
- Number of patients who discontinued emapalumab treatment for safety reasons.

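### The SAP omits the protocol's change-from-baseline and marked-abnormality laboratory summaries, so no table measures further worsening in patients already out of range at entry

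*SAP*

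**What the plan says.** Protocol 11.3.2 says that for each laboratory test "individual patient values will be listed and summarized and change from pre-treatment baseline values calculated and summarized". It adds: "Summaries of marked abnormalities and shift tables or boxplots will be tabulated for each laboratory test".

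SAP 10.2.1 specifies three outputs. The first is a shift table of "The number of patients with clinical laboratory values below, within, or above the normal range by visit and in relation to baseline", with percentages taken over the whole All Treated Analysis Set. The second is graphical: "Box and whisker plots for each parameter under clinical chemistry, hematology and coagulation will be produced to display absolute values over time". The third is listings by patient and visit, with out-of-range values flagged and pre- and post-conditioning marked.

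SAP Section 11, which records departures from the protocol's analyses, says nothing about laboratory data.

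SAP 2.2.2 makes this one of three safety endpoints: "Evolution of relevant laboratory parameters, e.g., complete blood cell (CBC) count, liver and renal function tests, and coagulation parameters".

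**The concern.** A three-category table registers a change only when a value crosses a limit of normal. Movement further out in the same direction stays in the same cell. Protocol 4.1.1 lists cytopenia, high ferritin and low fibrinogen among the HLH-2004 diagnostic criteria, so many children may start out of range on these tests. Their further deterioration is where a safety reader would look first, and it is what the two missing summaries would have described.

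The AE tables are a narrow second route. Protocol 9.2.4 says that laboratory abnormalities counted as HLH signs "will not be reported as AEs. If laboratory abnormalities are indicative of an HLH reactivation or worsening", and goes on to make the reactivation or worsening itself the reported event. A falling count can therefore be recorded as disease, with no table giving its depth. The protocol's risk section states: "Importantly, emapalumab treatment has not been associated with myelosuppression". A reader of the study report would want a table that bears on that statement in children who were cytopenic at entry.

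**Working it through.** The plan gives no figure on this point, so the check is a comparison of texts followed by a small illustration.

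**Step 1. Protocol 11.3.2 against the SAP's planned outputs.**

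| Protocol, per laboratory test | SAP counterpart |
|---|---|
| Values listed, out-of-range flagged | Present: Listings 16.2.8.1 to 16.2.8.3 |
| Values summarized | Graphically only: Figures 14.4.5.1 to 14.4.5.3 |
| Change from baseline summarized | None in 10.2.1, Table 15 or Table 17 |
| Marked abnormalities summarized | None in 10.2.1, Table 15 or Table 17 |
| Shift tables or boxplots | Both present |

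Table 15 has 3 domains (chemistry, hematology, coagulation) x 2 versions (overall, by treatment type) = 6 laboratory tables, 14.3.5.1.1 to 14.3.5.3.2. All six are shift tables.

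**Step 2. Does another part of the SAP supply the missing summaries?** Section 6.1.9.1 defines change from baseline, 6.1.10 gives rules for values beyond the quantitation limits in descriptive statistics, and Section 10 says safety data will be summarized descriptively. None of these is attached to a planned laboratory table. Where the SAP intends change-from-baseline tables it names them: the PedsQL tables, 14.2.8.1 to 14.2.9.7, are titled that way.

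**Step 3. What the shift table registers.** Assume a platelet normal range of 150 to 450 x10^9/L and a baseline of 90.

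- 90 to 80: below to below; (80 - 90)/90 = -11%
- 90 to 40: below to below; (40 - 90)/90 = -56%
- 90 to 10: below to below; (10 - 90)/90 = -89%

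Now assume 34 patients with baselines between 30 and 95, of whom 6 fall by 70% and 28 rise by 20%. The highest possible follow-up value is 95 x 1.2 = 114, still under 150, so the shift table shows 0 category changes. A change-from-baseline summary finds 6 falls of more than 50%, which is 6/34 = 18%. In one simulated set of this kind the boxplot of absolute values moved from median 58 to 54, lower quartile 44 to 38 and minimum 30 to 12. The fall is partly visible there, but it is not paired with baseline and gives no count of patients.

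**Step 4. What the AE route catches.** Under Protocol 9.2.1, anemia, neutropenia and thrombocytopenia are not separate AEs unless clearly due to something other than HLH. Under 9.2.4, other laboratory abnormalities become AEs only if they need intervention, change study medication or reach grade 4. A transaminase that is high at entry and rises to grade 3, meeting neither of the first two conditions and leading to no new diagnosis, is neither a laboratory AE nor a category shift.

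**The case against.** The strongest reply is that nothing is lost. Every value is listed, boxplots cover every parameter, grade 4 and intervention-triggered values enter the AE tables, HLH worsening is itself an AE, and a cytopenia clearly attributed to the drug is reportable. The protocol calls its statistical section an overview and leaves detail to the SAP. The SAP speaks of descriptive statistics for all safety data, and its table shells are a separate document not available here. The protocol also asks for shift tables or boxplots, and the SAP gives both.

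Much of this stands. A reader might infer that worsening cannot show at all in patients abnormal at entry. The documents do not support that, for the reasons just given. A reader might also take these abnormalities to be entry requirements. They are not: inclusion criterion 2 accepts a molecular diagnosis, a consistent family history or any five of eight criteria, and Protocol Table 4 provides for reactivated patients entering with only two or three abnormal features.

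What does not stand is the claim that the general sentences fill the gap. Listings are not summaries. Boxplots are unpaired, and the patients behind them change as children leave treatment. Unseen shells might carry extra columns, but all six table titles and the text of 10.2.1 describe shifts only. An overview in the protocol may be refined, yet dropping two named summaries is a change that Section 11 exists to record.

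**Conclusion.** The point holds in limited form. Two laboratory summaries promised by the protocol are missing from the SAP without declaration. As a result, no planned summary table counts or quantifies further same-direction worsening within patients who start out of range, on a named safety endpoint. It should be corrected; the primary analysis is not affected.

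The size in patients cannot be given. The documents contain no baseline distribution of laboratory values, and the 34-patient set above is an assumption chosen to show the mechanism. A reader might infer that only patients normal at baseline can contribute an adverse shift and turn that into a count. That fails as well, because a patient high at baseline can move to low, and the reverse.

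Nor do the documents support the inference that the study, as planned, cannot confirm or refute the statement on myelosuppression. The boxplots, listings and AE tables bear on it in part. The added tables would not settle it either, in a single-arm study that allows transfusion, G-CSF and etoposide.

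**What to change.** In SAP 10.2.1 and Table 15:

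- Add change-from-baseline summaries by visit for each laboratory test.
- Add a table of baseline grade against worst pre-conditioning on-treatment grade, using the modified WHO toxicity scale already named in Protocol 9.2.1 and 9.2.4. This can serve as the marked-abnormality summary.
- Flag values obtained under transfusion or G-CSF support.

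In SAP Section 11, declare and justify anything that stays omitted.

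The cost is SAP wording and a few descriptive tables. The laboratory values are already scheduled at each infusion visit, and transfusions are already listed (Listing 16.2.9.9). The downside is that the tables will also show disease-driven worsening and cannot attribute cause in a single-arm study, so they need a note saying so.

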10.2.2. Urinalysis

Urinalysis results will be listed only.

10.2.3. Cerebrospinal Fluid Data

The following information has been collected during the study with regard to CSF analysis:

- Protein
- RBC
- WBC
- Neopterin

All CSF data will be provided in data listings including comments on the results and reasons if not performed.

10.3. Vital Signs

Vital signs results will be presented in listings by patient number and visit. Values outside the normal range (+/-10%) and body temperature >= 37.5 Celsius will be flagged.

10.4. Physical examination

A by-patient listing will be provided for physical examination results by patient number and visit.

10.5. Electrocardiograms

ECG results will be presented in listings.

[figure not shown]
10.6. Imaging Test Results

A by-patient listing will be provided separately for abdominal ultrasound, chest examinations (including x-ray and CT) and brain examinations (including MRI and CT).

10.7. Systematic Search for Infections

Abnormal results of TB search as well as adenovirus, CMV, EBV and other specific infections assessed as medically relevant were to be recorded as AEs and will be presented in AE tables.

A by-patient listing will be provided with results from each infection search.

10.8. Hematopoietic Stem Cell Transplantation (HSCT)

A by-patient listing will be provided including patients undergoing HSCT with regards to:

- Date of start of conditioning / HSCT
- Stem cell source
- Graft manipulation
- Donor type.

10.9. Concomitant Medications and Procedures

Prior medication/therapy is defined as any medication/therapy with an end date prior to the first emapalumab infusion date or recorded with ongoing = 'No', if the end date is unknown. A concomitant medication is defined as a medication taken on or after the first dose of study drug (start date/time is on or after the first dose of study medication, end date/time is after the first dose of study drug), or recorded with ongoing = 'Yes', if the end date is unknown. If a medication starts prior to the date of first dose and continues after the date of first dose it will be considered both prior and concomitant.

Prior and concomitant medications will be summarized descriptively using counts and percentages as specified in Table 3. Summary tables of concomitant steroid use and concomitant HLH treatment (from the time of the first emapalumab infusion) will be provided.

Prior medications will be presented separately from concomitant medications. Prior medications will be split by previous HLH treatment and previous medications other than HLH treatment. Concomitant medications will be split by concomitant medications for HLH treatment and concomitant medications other than HLH treatment.

[figure not shown]
The frequency and percentage of medications will be summarized by ATC level 2 within level 1 by treatment groups, unless otherwise specified.

Prior and concomitant medications will be presented in listings. Prior and concomitant procedures will be listed separately and defined similarly as specified for prior and concomitant medications.

11. Changes from Planned Analysis

A summary of the changes with respect to analyses described in the study protocol is given below:

- Protocol Violations and Deviations terminology of major protocol deviations is used in the protocol. Due to an update in regulations ICH E3 Q&A R1 and ICH GCP E6 R2 terminology of important and non-important will be used when referring to protocol deviation classification from a study conduct perspective.
- Pharmacokinetic endpoints- population PK analysis will not be conducted as part of this

study. However, data from this study might be used in combination with data from other studies to refine existing population PK models.

- Pharmacodynamic endpoints- Population PK/PD analysis using non-linear mixed effects modelling will not be conducted as part of this study. However, data from this study might be used in combination with data from other studies to refine existing population PK/PD models. As part of the SAP, only PD parameters (i.e., concentrations) will be reported descriptively.
- Secondary efficacy endpoint: cumulative duration of response has been added to protocol specified endpoints.
- 'Evaluable Analysis Set Without Major Protocol Deviations' added which contains patients in the Evaluable analysis set who do not have a major protocol deviation that is deemed to have an impact on the statistical analysis.
- Sensitivity analysis 5 added where the overall response at EOT or Week 8 (whichever occurs earlier) is displayed based on patients in the 'Evaluable Analysis Set Without Major Protocol Deviations'.
- Supplementary analysis added where the overall response at EOT or Week 8 (whichever occurs earlier) is derived checking the number of abnormalities at baseline and the number of HLH criteria which worsen from baseline.

12. Other Planned Analysis

12.1. Pharmacokinetic/Pharmacodynamic/Immunogenicity Analysis

[figure not shown]
Descriptive summaries per timepoint of the serum concentration of emapalumab, PD parameters and ADAs (if any), as well as corresponding listings including CSF analysis or other matrices as applicable, will be provided in TLFs of this SAP.

Descriptive summaries of the following results will be presented in appropriate graphical analysis and tables for the All Treated Analysis Set:

- Levels of circulating total IFNγ (free IFNγ + bound to emapalumab) after initiation of emapalumab treatment.
- Levels of the main IFNγ-induced chemokines (CXCL9, CXCL10).
- Levels of other potential disease biomarkers.
- Level (if any) of circulating antibodies against emapalumab (ADAs).
- Serum concentration of emapalumab.
- Levels of serum sCD25

13. References

 US Federal Register. (1998) International Conference on Harmonization; Guidance on Statistical Principles for Clinical Trials. Department of Health and Human Services: Food and Drug Administration [Docket No. 97D-0174]. Federal Register Volume 63, Number 179,

pages 49583-49598. September 16, 1998.

- 2. ASA. (2016) Ethical Guidelines for Statistical Practice. Prepared by the Committee on Professional Ethics, April 2016. http://www.amstat.org/about/ethicalguidelines.cfm
- 3. RSS. (2014) The Royal Statistical Society: Code of Conduct, 2014.

14. Tables, Listings, and Figures

All listings, tables, and graphs will have a header showing the sponsor company name and protocol and a footer showing the version of SAS, the file name and path, and the source of the data (CRF page or listing number).

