i Chest X-ray: to be performed at pre-conditioning and then only if clinically indicated. Other imaging modalities (e.g. CT) performed as part of pre-transplant work-up are also acceptable.

^j **Abdominal ultrasound:** must include longitudinal measure of spleen

k PK/PD: in patients who receive HSCT, assessment of PK/PD to be also performed at D+3 after HSCT

¹ PK: if serum levels of emapalumab were detectable at the previous visit; PD: if serum levels of emapalumab were detectable at the previous visit; thereafter only if clinically indicated

mTB: as clinically indicated, at minimum at D+30, D+60, D+100, 6 month and 1 year/WD visits; until serum levels of emapalumab are no longer detectable

[&]quot;AE recording: all AEs are collected after signing of ICF up to Study Completion or until serum levels of emapalumab are no longer detectable (whichever occurs first). After elimination of emapalumab only SAEs will be reported.

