8.6.2 Follow-Up Post-HSCT (or After Last Emapalumab Infusion)

The following assessments will be performed at weekly visits after either HSCT or last emapalumab infusion (as applicable) until Day 30, and subsequently at Day 60, Day 100, and Month 6:

(In addition to the below, in patients undergoing HSCT, PK/PD samples will be collected at Day 3 post-transplant).

Clinical Assessment:

- Vital signs, including body temperature, heart rate, blood pressure, and oxygen saturation
- Physical examination, including as a minimum, spleen and liver size (by abdominal palpation), height/length (at 6 month visit only) and neurological examination
- Post HSCT outcome, if applicable
- Survival
- QOL questionnaires PedsQL[™], Pediatric Quality of Life Inventory[™] and BASES if HSCT is performed (at Day 30, Day 100 and Month 6 visits)

Laboratory:

- CBC with differential count (including large unstained cells count, whenever performed as routine)
- Coagulation tests: activated partial thromboplastin time and/or ratio, prothrombin time and/or INR, D-dimers, and fibrinogen

Study NI-0501-09 NI-0501 in Primary HLH Page 56 of 92

- Biochemistry: glucose, ferritin, CRP, liver function (AST, ALT, γGT, LDH, ALP, bilirubin), renal function (albumin, creatinine and urea) and triglycerides (fasting whenever possible)
- Urinalysis: glucose, blood, protein and/or albumin, leucocytes, ketones, pH, gravity

Search for infections:

- TB by PCR in any relevant specimen, as clinically indicated, at minimum at D+30, D+60, D+100, 6 month and 1 year/WD visits; until serum levels of emapalumab are no longer detectable
- Infection search & monitoring according to the patient's clinical presentation – in case of suspicion of infection

Imaging:

- Chest X-ray in case of clinical suspicion of pulmonary infection or to monitor existing abnormalities
- Abdominal ultrasound with spleen longitudinal measure (at Day 100 visit only)

Safety:

 Recording of any AEs occurred since last visit until serum levels of emapalumab are no longer detectable. After elimination of emapalumab only SAEs will be reported.

PK:

 Emapalumab concentrations (if serum levels of emapalumab were still measurable at the previous visit). Also at D+3 after HSCT, if performed

PD:

 CXCL9, CXCL10, sCD25, total IFNy (if serum levels of emapalumab were still measurable at the previous visit; then only if clinically indicated). Also at D+3 after HSCT, if performed

Immunogenicity:

Assessment for ADAs (at Day 100 visit only)

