8.6.3 End of Study: 1-Year Visit Post-HSCT (or After Last Emapalumab Infusion)/Withdrawal Visit

This visit represents the last visit of the study. The following assessments will be performed:

Clinical Assessment:

- Vital signs, including body temperature, heart rate, blood pressure, and oxygen saturation
- Physical examination, including as a minimum, spleen and liver size (by abdominal palpation), and neurological examination
- Post HSCT outcome, if applicable
- Survival
- QOL questionnaires PedsQL™, Pediatric Quality of Life Inventory™ and BASES if HSCT is performed

Laboratory:

- CBC with differential (including large unstained cells count, whenever performed as routine)
- Coagulation tests: activated partial thromboplastin time and/or ratio, prothrombin time and/or INR, D-dimers, and fibrinogen

Study NI-0501-09 NI-0501 in Primary HLH Page 57 of 92

•	Biochemistry: glucose, ferritin, CRP, liver function (AST, ALT, γGT,
	LDH, ALP, bilirubin), renal function (albumin, creatinine and urea)
	and triglycerides (fasting whenever possible)

Urinalysis: glucose, blood, protein, leucocytes, ketones, pH, gravity

Search for infections:

PK:

- TB by PCR in any relevant specimen (if serum levels of emapalumab were still measurable at the previous visit)
- Infection search & monitoring according to the patient's clinical presentation – in case of suspicion of infection

Imaging: • Abdominal ultrasound with spleen longitudinal measure

Safety:

Recording of any AEs occurred since last visit until serum levels of emapalumab are no longer detectable. After elimination of

emapalumab only SAEs will be reported.

Emapalumab concentrations (if serum levels of emapalumab were

still measurable at the previous visit)

PD: CXCL9, CXCL10, sCD25, total IFNγ (if serum levels of emapalumab

were still measurable at the previous visit, or if clinically indicated)

Immunogenicity: • Assessment for ADAs

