For laboratory results, as well as pharmacokinetic and pharmacodynamic results, with values below the lower limit of quantitation (i.e. < LLOQ), values will be imputed to zeros when summarizing for descriptive statistics and presented as "Below LLOQ" in listings. Values above the upper limit of quantitation (i.e. > ULOQ) for individual values will be imputed to ULOQ values when summarizing for descriptive statistics and presented as "Above ULOQ" in listings.

Pharmacokinetic/Pharmacodynamic/Immunogenicity parameters

For PK, PD and ADA the primary samples should be used in analyses, unless there is a reason (e.g., sample mishandling or bioanalytical reason) for the primary data to be considered invalid, in which case the back-up sample will be utilized. All results will be listed.

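### Late follow-up PK means are labelled All Treated but leave out patients whose drug has cleared, so they overstate concentration by about 1/(share still sampled); late PD means are selected too, in an unknown direction

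*SAP*

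**What the plan says.** **Sampling.** Protocol Table 2, footnote l, covers D+60, D+100, 6 months and 1 year: "PK: if serum levels of emapalumab were detectable at the previous visit; PD: if serum levels of emapalumab were detectable at the previous visit". For PD it adds "thereafter only if clinically indicated". Section 8.6.2 states the PK condition as "Emapalumab concentrations (if serum levels of emapalumab were still measurable at the previous visit") and the PD condition as "still measurable at the previous visit; then only if clinically indicated". Section 8.6.3 lets 1-year PD samples be taken if drug levels "were still measurable at the previous visit, or if clinically indicated".

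Table 2 and section 8.6.2 differ on where the condition starts. Table 2 leaves the weekly and D+30 samples free of it. Section 8.6.2 attaches it to its whole list of visits, which begins with the weekly ones.

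**Analysis.** SAP 12.1 asks for "Descriptive summaries per timepoint of the serum concentration of emapalumab, PD parameters and ADAs (if any"), by table and graph, for the All Treated Analysis Set. SAP Tables 14.3.6.4 (serum concentration) and 14.3.6.5 (PD) carry that population label. SAP 4.1 computes the mean, SD, median, minimum and maximum on non-missing values. For results below LLOQ, SAP 6.1.10 says "values will be imputed to zeros when summarizing for descriptive statistics". That rule is written for results, so it reaches measured samples only. The imputation rules in SAP 6.1.4 concern response parameters and dropouts, not PK or PD.

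**The concern.** The same state, no measurable drug, is handled in two ways. At the visit where clearance is found, the patient contributes zero. At the next visit no sample is taken, precisely because the drug had gone, and the patient counts as missing. The later PK mean then describes slow eliminators under a label that says All Treated.

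For PD the remaining values come through two different doors: patients who still carry drug, and cleared patients sampled because of their clinical condition. One mean mixes both.

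Further evaluation of PK and PD is a stated objective (protocol section 2, SAP 2.1). SAP section 11 removes from this study the population PK and PK/PD models that protocol 7.3 and 7.4 had planned. The descriptive summaries are therefore the study's own planned PK/PD report. A reader would take from them that drug persists longer in the treated population than it does.

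**Working it through.** The documents state no figure for follow-up PK or PD, so there is none to reproduce.

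**PK, general result.** Inputs: the sampling rule (Table 2 footnote l), the zero rule (SAP 6.1.10), and f, the share of at-risk patients still sampled at a visit, which the documents do not give. Assume that a patient skipped after an undetectable result would again have been below LLOQ, and that undetectable means below LLOQ.

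- Mean as the SAP computes it: m, over the sampled share f.
- Mean over all at-risk patients, skipped samples as zero: f × m + (1 − f) × 0 = f × m.
- Ratio: m / (f × m) = 1/f.

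| f | ratio 1/f | n sampled of 34 (34 × f) |
|---|---|---|
| 1.00 | 1.00 | 34 |
| 0.90 | 1.11 | about 31 |
| 0.75 | 1.33 | about 26 |
| 0.50 | 2.0 | 17 |
| 0.25 | 4.0 | about 9 |
| 0.10 | 10 | about 3 |

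The 34 is the protocol's minimum number of treated patients; deaths and withdrawals are ignored. The ratio is 1 only if nobody has cleared the drug. The median cannot move the other way, since adding zeros can only lower it or leave it unchanged, but it does not follow the 1/f formula.

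**PK, illustration.** Every input here is assumed: mono-exponential decline, lognormal starting level with median 100 µg/mL and log-SD 0.7, lognormal half-life with log-SD 0.4, and the condition applied from D+60. Each cell gives the ratio of the sampled mean to the all-patient mean.

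| Median half-life | LLOQ (µg/mL) | D+100 | 6 months | 1 year |
|---|---|---|---|---|
| 5 days | 1 | about 12.6 (8% sampled) | – | – |
| 10 days | 1 | 1.71 (59% sampled) | 6.1 (16% sampled) | – |
| 10 days | 0.1 | 1.13 | 2.0 | – |
| 20 days | 1 | 1.04 | 1.35 | about 4.4 |

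Dashes mark cells not used here. The size swings widely with the assumptions; the upward direction does not.

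**PD.** A skipped PD value is unknown, so zero cannot stand in for it. Let a share f be drug-detectable with mean a, relative to a mean of 1 in all cleared patients. Let a share g of the cleared patients be sampled on clinical indication, with mean b.

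- Mean of sampled patients: [f × a + (1 − f) × g × b] / [f + (1 − f) × g].
- Mean of all patients: f × a + (1 − f).

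Examples, with all values assumed:

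- f = 0.25, a = 0.5, g = 0: sampled 0.5; all 0.125 + 0.75 = 0.875; ratio 0.57.
- f = 0.50, a = 0.5, g = 0.1, b = 3: sampled (0.25 + 0.15)/0.55 = 0.727; all 0.75; ratio 0.97.
- f = 0.25, a = 1, g = 0.2, b = 3: sampled (0.25 + 0.45)/0.40 = 1.75; all 1; ratio 1.75.

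Over f from 0.25 to 0.75, a of 0.5 or 1, and (g, b) of (0, 1), (0.1, 3) or (0.2, 3), the ratio runs from 0.57 to 1.75. The two selections can pull in opposite directions. Protocol 5.2 reports faster emapalumab clearance with higher IFNγ production, so patients still detectable may have lower IFNγ-driven markers. Samples taken on clinical indication may be higher.

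**The case against.** **It is descriptive, and n is shown.** SAP 2.2.3 confines PK/PD to descriptive statistics, SAP 4.1 prints n, and individual results are listed. As a description of the patients sampled, the summaries are correct. This stands in part: a falling n is visible. But n does not say why patients left, and SAP 4.1 defines missing as the set total minus the non-missing, which puts cleared patients together with deaths and withdrawals.

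**The size is unknown.** This stands. The blood-volume estimate in protocol section 8 supposes drug detectable at every timepoint, but that is a sampling-volume assumption, not a forecast of clearance.

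**The shells are not in hand.** SAP 12.1 does not name the follow-up timepoints, the visit windows in SAP 6.1.5 cover treatment visits only, and table shells are in a separate document (SAP 15.2). A footnote there could already label the subset. That would help, but nothing in the SAP text calls for one.

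**Imputed zeros were never measured.** This is fair, and is why the fix flags them and puts the detectable count beside them.

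**Two stronger readings are not supported.** A reader might infer that late biomarker levels will look too high; the PD calculation and protocol 5.2 show that the direction is open. A reader might also infer that AE recording, zoster prophylaxis or the vaccination rule is affected, since each runs until drug is no longer detectable. Those rules turn on the patient's own serum level, not on a table mean.

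**Conclusion.** The point holds for PK. Once any patient has cleared the drug, the SAP as written overstates the All Treated mean concentration at the conditional visits by about 1/(share still sampled). This rests on cleared patients staying below LLOQ until any re-treatment. The magnitude cannot be computed from the documents.

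For PD, the late means come from a selected mixture under an All Treated label, and the direction of any bias is indeterminate.

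The ADA summaries are not affected: Table 2 schedules ADA at D+100 and 1 year without the detectability condition. The primary endpoint, its test and every efficacy conclusion are untouched. The change is still worth making, because these summaries are the planned report on a stated objective.

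**What to change.** In SAP 12.1:

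1. **PK.** At each follow-up timepoint report n detectable over n at risk, where at risk means alive, in follow-up and in the same follow-up period, with a reset on re-treatment. In the All Treated summary, count a sample skipped after an undetectable result as below LLOQ (zero), flagged as not measured.
2. **PD.** Impute nothing. Keep clinically indicated samples out of the per-timepoint summaries, and list them or summarise them separately. Label the remaining summaries at conditional visits as the drug-detectable subset, with n.
3. **Timepoints.** Name the follow-up timepoints to be summarised. Protocol Table 2 and section 8.6.2 must be reconciled on where the condition starts, so that the conditional visits are known.

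The cost is SAP wording and a little programming, with no new samples. The late PD summaries will hold fewer values.
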